DWW will focus primarily on healthy lifestyle and the prevention of weight gain through change in diet and physical activity. The dietary changes include: 1) caloric restriction; 2) increases in daily consumption of fruits and vegetables; 3) reduction in saturated and trans fat intake; and 4) increase in low-fat dairy intake consistent with the DASH eating pattern.⁹ The goals of physical activity are increases to > 150 minutes per week of physical activity. The intervention emphasizes daily self-monitoring of type and quantity of foods, number of servings of fruits and vegetables, calories, and minutes of physical activity.

Our primary outcomes for this research are related to implementation, rather than effectiveness. A quasi-experimental pre-/post- design is appropriate. The outcomes of the DWW randomized trials previously conducted demonstrate effectiveness.

We will also collect data on direct and indirect costs of the interventions. This will provide guidance to future interventions as to the effectiveness and cost/benefit ratios of group counseling. Cost data--such as counselor hours needed and intervention materials and supplies--will be collected and reviewed by the study coordinator and CTSI finance team that administers NCDHR funding; these financial data are maintained on the NCDHR-CTSI shared private network folder. No participant-level cost-related data will be collected and no identifiers are needed for cost-related data. These costs are helpful in determining sustainability plans for community-based interventions.

Note about English language study materials prepared/submitted for this RSRB review

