Subjects will have 6-month and 18-month follow-up appointments via Zoom or videophone, to assess change since baseline as well as post-intervention outcomes. The one-on-one qualitative health interview with a researcher and the REDCap health survey will be repeated at the 6-month and 18-month time points (see English version of surveys included with this application). These visits do NOT require in-person contact; they are all virtual.

Modification July 13, 2023: For the 10 participants in the YMCA-based virtual intervention group: Due to funding for this study ending in September 2024, we propose here to change the final data collection appointment for these final 10 participants only, so their final appointment will be 12 months from enrollment instead of 18 months from enrollment. Study coordinators will use the same 18-month data collection measures forms at the 12-month appointment with these 10 participants.

Health Survey in REDCap (see Table 1 below): Some data collection will be carried out in sign language along with English text version on a REDCap survey. We have developed a special external module in REDCap in collaboration with the REDCap creators at Vanderbilt University, which allows all of our survey questions to have ASL video in addition to English text, as well as unique features such as color changes and text size changes for use with Deaf-Blind respondents. At the beginning of the survey, the subject chooses a “sign model” to guide them through the survey, based on their preferred language and/or communication style (ASL or English-based sign language). The REDCap survey also has the ability to show instructions on how to use the survey. Once the survey begins, each survey item and response is shown in sign language video, followed by the English text of the question and response choices. The respondent enters or clicks on their response (and has the option to skip the item if they do not want to respond) using the mouse or touch screen technology depending on what device they use. Respondents can choose a different sign model at any point in the survey, and English captions can be turned on or off at any time.

[figure not shown]

Table 1. Data collection measures with DWW subjects

Measure/Description	Baseline	6 mo	18 mo	Mode of Administration
Demographics				
Deaf demographics				
Health history	X	X	X	Computer-based survey in ASL
Healthcare access				
Weight loss history				

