Secondary Outcome #1: Participant-level outcome: Mean change from baseline to 6-months (post-intervention) in number of fruit and vegetable servings per day as measured by the Block fruit, vegetable, fiber screener

Description: The mean difference from pre to post intervention in self-reported fruit and vegetable servings per day (baseline servings/day - follow-up servings/day) as measured by the Block Fruit-Vegetable-Fiber Screener.

The Block Fruit-Vegetable-Fiber Screener is a 10-item scale with responses ranging from: (1) Less than 1/week to (5) 2+ a day. Higher scores reflect a better outcome.

Time Frame: baseline, 6 months (pre and post intervention)

Secondary Outcome #2: Participant-level outcome: Mean change from baseline to 6-months (post-intervention) in physical activity as reported on the International Physical Activity Question (IPAQ)

Description: The mean difference in self-reported physical activity levels over the past 7 days

Time Frame: baseline, 6 months (pre and post intervention)

Secondary Outcome #3: Participant-level outcome: Mean change from baseline to 6-months (post-intervention) in self-reported body weight, for participants with BMI above normal range

Description: The mean weight change (in kg) from pre to post-intervention, expressed as a percentage of baseline weight, for any participants with a BMI above 24.9 (above normal range)

Time Frame: baseline, 6 months (pre and post intervention)

In addition to data from the survey questions, the survey software also produces additional user data, including keystroke data indicating that a different sign model was chosen at any point during the survey, that the font size or video background color was changed, , the time taken to complete the survey, and other user data. We will use this keystroke data to examine user preferences, differences in how groups of respondents use the survey (e.g., older vs. younger respondents), and for quality improvement purposes.

Data Storage and Confidentiality.

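### Secondary Outcome #1 is headed as a change from baseline but calculated as baseline minus follow-up, so a gain in fruit and vegetable intake would be reported as a negative number

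*Combined protocol and SAP*

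**What the plan says.** Under Data Analysis and Monitoring in Section III of the combined protocol and SAP, Secondary Outcome #1 is titled "Mean change from baseline to 6-months (post-intervention) in number of fruit and vegetable servings per day". Its description opens with "The mean difference from pre to post intervention in self-reported fruit and vegetable servings per day" and then gives the subtraction in parentheses, so that the end of the phrase reads "self-reported fruit and vegetable servings per day (baseline servings/day - follow-up servings/day"). A little further on, the same entry says of the dietary screener: "Higher scores reflect a better outcome".

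Two other places bear on direction. The Overall study design section lists "increases in daily consumption of fruits and vegetables" among the dietary goals. The section on post-intervention data collection says that the follow-up visits are held "to assess change since baseline as well as post-intervention outcomes".

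Secondary Outcome #2 carries a title of the same form, "Mean change from baseline to 6-months (post-intervention) in physical activity as reported on the International Physical Activity Question (IPAQ"), as does Secondary Outcome #3 for body weight. Neither prints a subtraction order. The planned test for the dietary score is a paired t-test; whether it is one- or two-sided is not stated.

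**The concern.** The title and the pre-to-post wording are ordinarily read as follow-up minus baseline, yet the formula in the same sentence runs the other way. An analyst who follows the formula reports a number whose sign contradicts its own heading. One who follows the heading departs from the written formula. Two careful analysts could therefore report the same data with opposite signs.

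The likely misreading is not harmless. Someone who is told that higher screener scores are better, and who then sees a negative mean change from baseline, will naturally conclude that intake fell. Under the written formula it rose. Anyone who later extracts the result from a table would be exposed to the same mistake.

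The plan also intends to look for variables associated with change in the dietary score and to adjust for confounders by regression. If the printed order is carried into those models, their coefficients change sign too: a predictor of a larger gain in intake would have a negative coefficient.

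**Working it through.** The plan gives no expected effect, standard deviation, power or significance level for this outcome, so there is no figure of its own to reproduce. The check is one of sign.

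**Inputs from the document**
- Formula for Secondary Outcome #1: baseline minus follow-up servings per day.
- Intended effect: an increase in intake (Overall study design).
- Test: paired t-test (Data Analysis).
- Number of subjects: 108 (Section II).

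**Assumptions, not in the document**
- True mean increases of 0.5, 1.0 and 2.0 servings per day.
- SD of the change: 2 servings per day.
- Follow-up of either 100% or 70%; 0.70 × 108 = 75.6, taken as 76.
- A two-sided test and 95% confidence intervals.

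**Step 1: sign.** Let baseline intake be B and the true increase d > 0, so follow-up intake is B + d.
- Written formula: B − (B + d) = −d.
- Direction implied by the title: (B + d) − B = +d.

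For one participant going from 3 to 4 servings per day, the written formula gives 3 − 4 = −1, and the title implies 4 − 3 = +1.

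**Step 2: size of the discrepancy.** The two versions differ by 2d. This is not bias, because the absolute value is the same.

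| True mean increase | Written formula | Title direction | Difference |
|---|---|---|---|
| 0.5 | −0.5 | +0.5 | 1.0 |
| 1.0 | −1.0 | +1.0 | 2.0 |
| 2.0 | −2.0 | +2.0 | 4.0 |

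**Step 3: effect on the test.** The paired statistic is t = mean difference / (SD / √n). Reversing the subtraction changes the sign of the numerator and nothing else. With a mean increase of 1.0 and SD 2:
- n = 108: SE = 2/√108 = 0.192. t = −5.20 as written and +5.20 reversed; two-sided p = 9.8 × 10⁻⁷ either way. The 95% interval is −1.38 to −0.62 as written and 0.62 to 1.38 reversed.
- n = 76: SE = 2/√76 = 0.229. t = −4.36 as written and +4.36 reversed; two-sided p = 4.1 × 10⁻⁵ either way. The 95% interval is −1.46 to −0.54 as written and 0.54 to 1.46 reversed.

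**Step 4: is the convention explained elsewhere?** No section says that a negative difference means increased intake. The sentence saying that higher is better describes screener scores, not the difference, and if anything invites the reader to take a positive difference as improvement.

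**The case against.** The best reply is that nothing inferential is at stake. The subtraction order is printed directly beneath the title, so anyone who reads the definition can recover the direction. Either order measures the same quantity. The Data Analysis text describes the tests neutrally, as differences between baseline and later time points. The study has a single arm, so no between-group comparison can be reversed, and its primary outcomes are site-level implementation measures. If a label stating the direction would be enough, then the formula is awkward rather than wrong.

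Much of this stands. Magnitude, interval width and a two-sided p-value are untouched, and the illustrative t-tests serve only to show that. The purpose given for the follow-up visits is weak evidence, because it does not define the calculation. The silence of Outcomes #2 and #3 on subtraction order does not show that #1 is wrong; it shows only that no common convention has been set. The parenthesis might also have been meant merely to name the two paired values, although subtraction is the natural reading and nothing in the document supports the alternative.

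The reply does not remove the conflict inside the one definition. A title and a description that point one way, with a formula that points the other and no label to reconcile them, will yield a reported number that reads as the opposite of what happened.

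**Conclusion.** The concern holds. As written, Secondary Outcome #1 has the wrong sign for its own title: an increase of d servings per day would be reported as a change of −d. The formula is determinate, so this is an error of reporting direction in one secondary outcome and not a flaw in inference. It reaches the point estimate, any confidence limits, and the coefficients of any model that uses this change score. It does not reach the primary outcomes or the sample size.

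The sign conclusion needs no assumption beyond applying the formula literally. The statement that the p-value is unchanged assumes a two-sided test. A one-sided test coded in the wrong direction would be affected, though nothing in the plan suggests that one is intended.

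**What to change.** In the description of Secondary Outcome #1, define the change as 6-month minus baseline servings per day, so that a positive value is an increase in intake. Use the same direction in the paired analysis, in the models of change in the dietary score, and in every table that reports the outcome. If the present order is kept for any reason, state beside the definition and beside every reported result that negative values mean increased intake.

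This is a one-line correction. It has no cost for data collection, sample size or testing.

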- 7 **Vulnerable Subjects.** There are no special classes of individuals who may be considered vulnerable subjects that are targeted for enrollment in this study. Specific modifications have been made to make this study culturally and linguistically appropriate for use with Deaf participants. The researchers who have direct contact with study subjects, including the researchers who obtain informed consent and deliver the health intervention modules, will be fluent in ASL. This research includes the guidance of Deaf community advisory boards, whose members are deaf adult ASL-users. No children will be included in the research. Prisoners or institutionalized individuals will not participate in this research.

III. METHODS AND PROCEDURES

Overall study design

The overall design of the DWW Implementation Study will have up to nine sites hosting DWW in three cities. NCDHR is working with each site to establish a timeline for beginning the program; as each new site is added, we will upload their Letter of Cooperation as a Modification to our application (we will upload each Letter of Cooperation as an amendment, once they are received). It is important to note that these sites are NOT engaged in the research, as per the federal definition.

The total length of the full study at each site is about 18 months for individual participants (baseline and two follow-up data collection points). Interventions will consist of 16-week group counseling Zoom sessions led virtually by trained, ASL-fluent Deaf counselors. Following the

16-week intervention, subjects will enter a 6-month “maintenance phase” with less intense interventions. This study is by definition a single-arm interventional clinical trial; we will register this study on clinicaltrials.gov as required, and will submit a modification to enter the NCT number prior to conducting the study.

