<https://www.urmc.rochester.edu/health-information-management/roi-forms.aspx> . Once the subject completes this form, this will allow our study team to prepare the medical clearance letter that the subject will then give to their healthcare provider (the letter will state that the subject reports having a heart attack or stroke or weight loss surgery or pregnancy or BMI over 45.0). There are two levels of permission: one to obtain clearance to participate in the whole DWW intervention, and the other to participate only in the educational and dietary components (but be excluded from the physical activity components). Subjects will be required to obtain permission from their provider on their own (using the Physician Permission Form) and to return the completed form to the research team in order to participate in the relevant 16-week intervention component(s). These procedures were successfully implemented in the first two

clinical trials of Deaf Weight Wise; in fact, only a very small proportion of participants in the first two clinical trials needed permission from their provider based on their screening answers, and were able to successfully get that permission.

At the time of enrollment/baseline appointment, we will still enroll the subject even if medical clearance is required for the DWW intervention component. If the subject does not obtain medical clearance before their 16-week zoom-based intervention begins, the research team will consult with the PI ([name] is also a physician) to determine whether participation should be halted entirely or whether the subject should be encouraged to not engage in the exercise or diet modification components. There are no other language-accessible health intervention programs for Deaf sign language users available. If we decline enrollment entirely based on needing provider permission for only those with a health issue, this team feels it is a missed opportunity for these Deaf participant(s), given the minimal risk nature of the study and the benefit to promoting healthy lifestyle. However, if we allow enrollment at the point of screening, and then await provider permission before the intervention starts, we help to ensure that these Deaf participants will not have missed an opportunity to participate. Based on the timing of each site's enrollment, there may not otherwise be an opportunity for these particular Deaf participant(s) in the future if we decline enrollment at that point of screening.

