Income-restricted apartment complex	Rochester View Apartments
Community organizations -- mainstream	YMCA of Greater Rochester
Workplace wellness programs	Better Me, Rochester Institute of Technology
Clinical-community linkages	Deaf Wellness Center, URMC

NCDHR is working with each site to establish a timeline for beginning the program; as each new site is added, we will upload their Letter of Cooperation as a Modification to our application (see one Letter of Cooperation included with our application to date).

NCDHR research coordinators who have also been DWW counselors will train a new DWW counselor(s) at each of these partner sites, so that they can implement DWW within their own agencies/communities. The DWW intervention has been studied as an in-person group intervention, and also as a 1-on-1 individual video remote intervention. Due to the COVID-19 pandemic and the need to have remote participation with no in-person contact, we have adapted the DWW intervention to be held in a group format over Zoom, with a DWW counselor and several subjects meeting virtually. Partner sites will begin the DWW intervention sequentially in a staggered timeline, depending on when the site is prepared to start the intervention and once a counselor has been identified and trained. Not all DWW groups will run at the same time; we expect small groups of subjects to be enrolled at the different sites over a period of 12-18 months.

Update as of 5/2/2022: We have established a work flow for intervention counselors, with University of Rochester Purchasing. Deaf Weight Wise intervention counselors will become approved independent contractors with University of Rochester. The counselors are NOT working for the implementation partner sites, and therefore the implementation partner sites are not engaged in the research. All intervention counselors will be approved contractors. All counselors will complete the required CITI training and will be added to this study application as external team members. See page 12 of the protocol for a description of other Training the counselors will receive from this study team. Counselors will have weekly and if needed, daily oversight from NCDHR Lead Counselors as well as the Deputy Director/Study Coordinator of this study team, to assist with any issues that arise. Counselors will not be supervised by anyone at the external partner implementation sites (the sites are only assisting with recruitment as per their letters of cooperation).

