Group Intervention (total expected N = 90 (approximately 10 subjects at each site):

The DWW group intervention will consist of groups of approximately 5 subjects who meet together for 16 weeks, for two hours each week. Group meetings will be held virtually on Zoom.

A trained, deaf, ASL-fluent DWW counselor will lead the sessions. We estimate that up to 18 groups will be established during the study period, with each site running two intervention groups (5 subjects in each Zoom group). As we match subjects' and counselors' schedules, our intervention group sizes may range slightly in size. Subjects will be encouraged to continue with the same group throughout the 16 week program, to take best advantages of social interactions and group dynamics.

Selected sessions of the DWW Curriculum are included in this application; select counselor lesson plans/guides and counselor powerpoint presentations are also included. Subjects will be asked to complete a daily food and physical activity diary during the course of the 16-week intervention (via the MyFitnessPal online app or MyFitnessPal website, or via the DWW Subject Food Diary uploaded in the application). Subjects will complete a food diary using MyFitnessPal, or a "calorie counter" book called "The Calorie King." Each intervention session will include group sharing and problem solving, discussion of a weight management topic, which may include watching a powerpoint presentation and/or ASL video; and a discussion on goal setting and action planning for the next week. A key principle of the DWW Curriculum is motivational interviewing, in which the counselor acts as a facilitator to: 1) help participants identify/recognize their own unhealthy behaviors, 2) help individuals build skills that will promote behavior change, and 3) help group members to support each other to make behavior changes. The Curriculum includes group exercise activities ("Do It!"), experiential learning activities ("Try It!" such as learning how to read a nutrition label or modify a recipe to make it healthier), and group activities related to food preparation or encouraging of trying new recipes and healthy foods ("Taste It!").

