At weeks 6, 11, and 16, each subject receives a Personal Feedback Report [see template included with the curriculum] which reviews their physical activity and food consumption diaries and their weight changes. By the end of the 16-week curriculum, each individual will have approximately 32 hours of group contact time.

During the DWW 16-week intervention, each enrolled subject will be provided a scale for them to keep at home. They will use the scale to report their weight during 16-weeks intervention, 6-month maintenance period, and 6-mth and 18-mth follow up appointments.

Over the course of the 16 week intervention, subjects will be able to earn points for attendance, completeness of their food and physical activity diary, for including calorie counts on at least 6 days per week, and for meeting physical activity requirements for the week. Subjects will be able to redeem these points (called "Wisebucks") at three different sessions (sessions 6, 11, and 16) for a variety of items including water bottles, adjustable measuring spoons, and other prizes related to the purpose of DWW.

The group maintenance phase starts immediately after the 16-week intervention, and consists of two meetings of the original group via Zoom; one at month 3 of the 6-month maintenance period and one at month 6 of the 6-month maintenance period. This will again consist of review of self-monitored diet and physical activity, problem solving and goal setting/action planning for their long-term program. Group attendees will be encouraged to interact with their group members during the intervention and maintenance phases. Each person will receive videophone or Zoom calls/reinforcements during each month of the 6-month maintenance

period. Counselors will also email participants bi-weekly to check in with participants and provide additional support.

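### Could the 6-month visit used for Secondary Outcomes #1-#3 fall before the 16-week course has ended?

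*Combined protocol and SAP*

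**What the plan says.** Under Data Analysis and Monitoring, the three participant-level secondary outcomes (fruit and vegetable servings, IPAQ physical activity, and percentage weight change in participants above the normal BMI range) carry the same line: "Time Frame: baseline, 6 months (pre and post intervention".

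The section on post-intervention data collection sets two virtual follow-up visits, at 6 and 18 months, meant to measure both change from baseline and outcomes after the course. Overall study design gives the length of participation as "about 18 months for individual participants (baseline and two follow-up data collection points". The final visit is explicitly counted from enrollment (the July 2023 modification, repeated in V.2 Process of Consent, and V.1 on recruitment). The anchor of the 6-month visit is not stated.

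The course has its own clock. Under Group Intervention it is delivered to "groups of approximately 5 subjects who meet together for 16 weeks, for two hours each week". Under Intervention Description, "Partner sites will begin the DWW intervention sequentially in a staggered timeline, depending on when the site is prepared to start the intervention". What comes next is also fixed: "The group maintenance phase starts immediately after the 16-week intervention".

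**The concern.** The outcome definitions treat two things as one: a calendar visit at 6 months and a measurement after the course. They coincide only if the course is over by then. Enrollment precedes session 1 by design, and the text available gives no maximum wait, no window for the 6-month visit, no link from that visit to session 16, and no analysis rule for an early visit.

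If some visits were early, partial exposure would be recorded as the post-course value in all three outcomes. Start dates are set site by site, so timing could also become entangled with site in the planned look at heterogeneity and in the Aim 4 associations with fidelity. In a single-arm pre/post design, no concurrent control group absorbs such differences.

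**Working it through.** The plan states no figure on this point, so there is nothing to reproduce. The check is calendar arithmetic.

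**Inputs**
- Six months = 365.25 / 2 / 7 = 26.09 weeks.
- Sixteen weekly sessions (Group Intervention), so session 16 falls 15 weeks after session 1.
- Assumptions: the 6-month visit is counted from enrollment, and no week is skipped. Each skipped week removes one week of slack.

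**Longest wait that still puts the visit after the course**
- To session 16: 26.09 - 15 = 11.09 weeks.
- Counting 16 full weeks: 26.09 - 16 = 10.09 weeks.
- Taking six months as 24 weeks: 24 - 15 = 9 weeks.

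**Position of the visit by wait**

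Sessions held = min(16, floor(26.09 - wait) + 1). Weeks since session 16 = 26.09 - wait - 15.

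| Wait (weeks) | Sessions held | Weeks since session 16 |
|---|---|---|
| 0 | 16 | 11.1 |
| 4 | 16 | 7.1 |
| 8 | 16 | 3.1 |
| 11 | 16 | 0.1 |
| 12 | 15 | -0.9 |
| 16 | 11 | -4.9 |
| 20 | 7 | -8.9 |

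**The one group with dates (YMCA)**

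The course starts in mid-August 2023, taken here as 15 August. V.9 gives enrollment as July-August 2023; the modification is dated 13 July.
- From 13 July: 33 days / 7 = 4.7 weeks' wait; the visit falls 26.09 - 15 - 4.7 = 6.4 weeks after session 16.
- From 1 July: 45 days / 7 = 6.4 weeks' wait; the visit falls 26.09 - 15 - 6.4 = 4.7 weeks after session 16.

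**Enrollment deadline for the other sites**

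V.1 sets 18 January 2023. Six months later is 18 July 2023, and 15 weeks before that is 4 April 2023. Someone enrolled on the deadline would have an early visit only if session 1 came after 4 April 2023 (28 March if 16 full weeks are counted).

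**Do the suggested causes of delay hold?**
- *Medical clearance.* The protocol describes the benefit "if we allow enrollment at the point of screening, and then await provider permission before the intervention starts". That shows enrollment before session 1, not a longer wait. The same section makes the course start the deadline: without clearance by then, the team consults the PI about limited or halted participation. It also says few participants needed clearance in the earlier trials.
- *Staggered sites.* The same paragraph expects enrollment, too, to be spread across sites over 12-18 months. If both move together, staggering creates no gap between them.
- *Group formation.* Primary Outcome #1 refers to implementation after at least 5 enrollments at a site, and V.1 reports low enrollment in Buffalo and Syracuse. This is the plausible route. If a group started as soon as the fifth person enrolled, the first would wait four gaps, so an early visit needs an average gap above 11.09 / 4 = 2.8 weeks; for the second enrollee it is 11.09 / 3 = 3.7 weeks. The documents give no enrollment rate to set against these.

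**The case for a change.** The strongest case for a change does not depend on any early visit. Waits of 0 to 11 weeks put the visit 11 to 0 weeks after session 16, so one label covers people just finishing the course and people with 2 to 3 months of maintenance contact, including monthly calls and "Counselors will also email participants bi-weekly to check in with participants and provide additional support". If coordinators delay visits so that they follow the course, six months is no longer fixed. If they do not, the post-course label is not guaranteed. The plan does not say which gives way, and a sentence and a table would settle it.

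The gap in the text is real, and slow group formation in two regions could have produced long waits. The rest is weaker. A spread of weeks after treatment is ordinary for a visit fixed in calendar time, and the prespecified estimate is change at 6 months. The section heading and the outcome titles make the intended order clear. The counselor enters weekly attendance, weight and diary summaries in REDCap (Data management by the DWW counselor), so an analyst can place session 16 relative to each visit, provided the entries are dated, which the protocol does not say. Weekly debriefings also monitor adherence to the protocol. The study information sheet, which shows a timeline, is not among the documents and may state the anchor.

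**Conclusion.** The concern does not call for a change. It identifies a missing detail, not an error. The 6-month visit would precede session 16 only after a wait of more than about 11 weeks (10 on the stricter count). No document shows such a wait, and the datable group is inside the limit by 4.7 to 6.4 weeks. No figure is given for the effect on the mean changes: the share of early visits and the response at partial exposure are both unknown, as is the direction of any bias.

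Little would be gained by amending. If the January 2023 deadline held, 6-month visits outside the YMCA group were due by about 18 July 2023, five days after the date of this version, so a scheduling rule could hardly affect them. The main paired comparison would stay as it is in any case. Reporting weeks from session 16 to the visit, and checking results without any early visits should there be some, is ordinary analytic practice that the plan already permits.

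This conclusion assumes that visits are counted from enrollment, that sessions ran weekly without long breaks, and that session dates can be recovered. Evidence of many waits beyond 11 weeks would reopen the question for the secondary outcomes only.
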